5.7 Source data

All information contained in the medical history, nurse registrations, and complementary exploration reports, such as, but not limited to, laboratory test, physical assessments (2MWD, 6MWD, muscle strength, walking activity), subject self-reporting questionnaires (SF-36, VAS for pain and FSS), and specific study data sheets, will be considered as source data.

For every single individual enrolled, the Investigator will record the clinical trial title, EudraCT number and sponsor (Instituto Grifols, S.A.), as well as the inclusion date and the randomization number, into the subject's medical history.

The Investigator will be responsible for maintaining complete and adequate case histories in source records of each subject. Source data must be preserved, at least, for the maximum period requested by local regulations and made available by the Investigator in case of inspection or audit.

The intended location for source data should be clearly defined and documented. This document should be signed by the principal investigator and filed in the investigator's trial master file.

SELECTION AND WITHDRAWAL OF SUBJECTS

6.1 Clinical trial subject inclusion criteria

Subjects fulfilling the following criteria at the SV and the EV/IV1 are eligible for participation in the study:

- 1. Male or female aged 18 to 75 years.
- 2. Subjects who understand and voluntarily signed and dated the Clinical Trial Written Informed Consent Form for his/her clinical trial participation.
- 3. Subjects with a BMI less than 35 kg/m².
- 4. Subjects who meet the clinical criteria for diagnosis of PSS as set by the March of Dimes [69] (ANNEX 17).
- 5. Subjects who are ambulatory or are able to walk with a cane or other aids or use a wheelchair (but they are not wheelchair-bound).
- 6. Subjects who have at least 2 newly weakened muscle groups due to PPS (as defined by medical history), with at least one of them in a lower extremity, and having an MRC scale score greater than 3 at the MMT performed by the independent assessor at the SV.
- 7. Female subjects of child-bearing potential[†] must have a negative test for pregnancy (HCG-based assay).
- 8. Female subjects of child-bearing potential and their sexual partners have agreed to practice contraception using a method of proven reliability (i.e., hormonal methods; barrier methods; intrauterine devices methods) to prevent a pregnancy during the course of the clinical trial.

- 9. Subjects must be willing to comply with all aspects of the clinical trial protocol, including blood sampling and long-term storage of extra samples for the entire duration of the study.
- 10. Subjects who are able to walk a 2MWD of at least 50 meters at the SV and EV/IV1.
- 11. Subjects who are able to walk a consistent baseline 2MWD, that is, the difference in 2MWD between the SV and EV/IV1 is not more than 10%.

[†]Women of child-bearing potential include any female who has experienced menarche and who has not undergone successful surgical sterilization (hysterectomy, bilateral tubal ligation or bilateral oophorectomy) or is not postmenopausal (postmenopausal is defined as amenorrhea for more than 12 consecutive months or women on hormone replacement therapy with documented serum follicle stimulating hormone level < 35 mIU/mL). Even in women who are using oral, implanted or injectable contraceptive hormones or mechanical products such as an intrauterine device or barrier methods to prevent pregnancy or practicing abstinence or where their sexual partner is sterile, e.g., vasectomy, should be considered to be of child-bearing potential.

6.2 Clinical trial subject exclusion criteria

Subjects who meet any of the following criteria at the SV and EV/IV1 are excluded from study participation:

- 1. Subjects who have received human normal immune globulin treatment given by intravenous, subcutaneous or intramuscular route within the last 3 years.
- 2. Subjects who are not ambulatory (wheelchair-bound individuals).
- 3. Subjects with poor venous access.
- 4. Subjects with intractable pain requiring narcotics or other psychotropic drugs.
- 5. Subjects with a history of anaphylactic reactions or severe reactions to any blood-derived product.
- 6. Subjects with a history of intolerance to any component of the investigational products, such as sorbitol.
- 7. Subjects who are receiving corticosteroids, except for those who are taking inhaled corticosteroids for asthma.
- 8. Subjects with a documented diagnosis of hyperviscosity or hypercoagulable state or thrombotic complications to polyclonal IVIG therapy in the past.
- 9. Subjects with a history of recent (within the last year) myocardial infarction, stroke, or uncontrolled hypertension.
- 10. Subjects who suffer from congestive heart failure, embolism, or ECG changes indicative of unstable angina or atrial fibrillation.
- 11. Subjects with a history of chronic alcoholism or illicit drug abuse (addiction) in the preceding 12 months prior to the SV.
- 12. Subjects with active psychiatric illness that interferes with compliance or communication with health care personnel.
- 13. Subjects with depression with scores >30 as assessed by the CESD validated scale.

CKIFOLS

- 14. Females who are pregnant or are nursing an infant child.
- 15. Subjects with any medical condition which makes the clinical trial participation unadvisable, or which is likely to interfere with the evaluation of the study treatment and/or the satisfactory conduct of the clinical trial according to the Investigator's judgment.
- 16. Subjects currently receiving, or have received within 3 months prior to the SV, any investigational medicinal product or device.
- 17. Subjects who are unlikely to adhere the protocol requirements, or are likely to be uncooperative, or unable to provide a storage serum/plasma sample prior to the first investigational drug infusion.
- 18. Subjects with a known selective IgA deficiency and serum antibodies anti-IgA.
- 19. Subjects with renal impairment (*i.e.*, serum creatinine exceeds more than 1.5 times the upper limit of normal [ULN] for the expected normal range for the testing laboratory).
- 20. Subjects with AST or ALT levels exceeding more than 2.5 times the ULN for the expected normal range for the testing laboratory.
- 21. Subjects with hemoglobin levels <10 g/dL, platelets levels <100,000 /mm³, white blood cells count <3.0 k/ μ L and ESR >50 mm/h or twice above normal.
- 22. Subjects with known seropositive to HCV, HIV-1 and/or HIV-2.
- 23. Subjects with a history of intolerance to fructose.

6.3 Subject withdrawal criteria and procedures

A subject's participation in the study may be terminated early under the following circumstances:

- 1. Subject withdraws the informed consent to participate in the clinical trial.
- 2. Subject does not meet all inclusion criteria.
- 3. Subject meets any of the exclusion criteria.
- 4. Subject is not able to adhere to the main protocol requirements (major protocol violations). Major protocol violations might include, but are not limited to, repeated missed infusions (more than 1 consecutive missed every 4 weeks infusion or more than 4 missed infusions per treatment period).
- The occurrence of an AE, which in the Investigator's opinion, requires the subject withdrawal from the clinical trial.
- 6. The occurrence of a confirmed thromboembolic event.
- 7. The occurrence of a confirmed clinically significant hemolysis event.
- 8. Undercurrent illness that could interfere in the study conduct or subject's safety might be threatened, at the Investigator's judgment.
- 9. Any event which in the Investigator's opinion impedes subject's participation in the study.
- 10. The subject is lost to follow-up (no attendance the scheduled study visits after randomization).

11. Subject's death.

If study participation is terminated due to an AE, the subject will be followed-up until the AE is resolved, or has been stabilized and no further change is expected, and the Investigator deems that further observations/examinations are no longer medically necessary.

If an individual is withdrawn from study due to pregnancy, the Medical Monitor must be informed by the site or by the Investigator. The pregnancy must be reported according to described procedures in Sections 9.3.8 and 9.4. If the subject had a spontaneous abortion then the event will be captured as a SAE.

Subjects who are discontinued early after randomization from the study will not be replaced.

Sites affected by the COVID-19 pandemic can refer to ANNEX 18 for extraordinary contingency measures to be implemented.

7 TREATMENT OF SUBJECTS

7.1 Treatments to be administered

During both stages of this clinical trial, each subject will receive intravenous infusions of investigational product (test or placebo) every 4 weeks during a treatment period of 52 weeks, with each dose being administered over a 2-consecutive-day dosing period (Day 1 and Day2) up to 13 infusions visits, that is, 26 intravenous infusions. A window period of \pm 1 week is allowed for any infusion after Infusion 1.

Flebogamma[®] 5% DIF (test) and Normal Saline Solution (placebo) will be used as investigational products.

Subjects randomized to the IVIG 2 g/kg arm will receive a total dose of 2 g/kg of body weight of Flebogamma[®] 5% DIF over 2 consecutive days (1 g/kg Day 1 and 1 g/kg Day 2). Subjects randomized to the IVIG 1 g/kg arm will receive a total dose of 1 g/kg of body weight of Flebogamma[®] 5% DIF on 1 day and, to maintain the blind, a total dose of 20 mL/kg of body weight Normal Saline Solution (equivalent volume of 1 g/kg of body weight Flebogamma[®] 5% DIF infusions) on a separate day, for a total dosing period of 2 consecutive days. The order of 1 g/kg of body weight of Flebogamma[®] 5% DIF or 20 mL/kg of body weight Normal Saline Solution infused on 2 consecutive days will be randomly determined for each subject by the Interactive Web Response System (IWRS), which will remain the same for the subject for all infusion visits during the treatment period.

Individuals randomized to the placebo (Normal Saline Solution) arm will receive a total dose of 40 mL/kg of body weight of Normal Saline Solution over 2 consecutive days (20 mL/kg infused on Day 1 and 20 mL/kg infused on Day 2).

7.1.1 Missed infusions processing

It is not allowed to prolong the treatment period. Infusions will not be postponed beyond their window period (\pm 1-week window period will be allowed for any infusion after Infusion 1).

A missed infusion will occur when a subject will not be administered with any dose of the investigational product at the scheduled infusion visit. If subject receives the investigational product at Day 1 but does NOT receive at Day 2, this will NOT be considered a missed visit.

Missed infusions will not be replaced.

During the treatment period, study subjects will be allowed to miss up to 1 consecutive infusion. More than 1 consecutive missed infusion is defined as a major protocol violation and requires subject withdrawal (Section 6.3).

A maximum of 4 missed infusions will be allowed during the treatment period (52 weeks). More than 4 missed infusions during the treatment period are defined as a major protocol violation and require subject withdrawal (Section 6.3).

Sites affected by the COVID-19 pandemic can refer to ANNEX 18 for extraordinary contingency measures to be implemented.

7.2 Medication(s)/treatment(s) permitted (including rescue medication) and not permitted before and/or during the trial

Study individuals will receive their routine therapy to treat their symptoms of PPS provided that the dose remains stable, or modified according to the standard of care and previously approved by the Investigator.

Subjects will not be allowed to receive any of the following study-specific prohibited medications: other investigational drug and human normal immunoglobulin therapy out of this clinical trial. In addition, subjects will not be allowed to receive any of the following study-specific prohibited medications unless considered medically necessary for the subject's welfare which might be given at the discretion of the investigator: narcotics or corticosteroids (except for inhaled corticosteroids taken for asthma, which will be allowed on-demand).

In any case, administration of all concomitant medication must be recorded in the appropriate section of the subject's eCRF.

No drug-drug interactions have been reported with the use of IVIG therapy.

To attenuate infusion-related events and to maintain blinding, all subjects will be pre-medicated 30-60 minutes prior to each investigational product infusion with 975-1000 mg of acetaminophen and 20-25 mg of diphenhydramine (or the equivalent dose of the available antihistaminic drug) provided no previous history of allergies to these medications is known. The use of the following drugs is not allowed as pre-infusion medication for investigational product administration: ASA; e.g., aspirin), NSAIDS, or corticosteroids (except for inhaled corticosteroids taken for asthma which will be allowed on-demand).

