4.4.2.3 Dosage regimen of investigational product (test and placebo)

At Stage 1, Flebogamma[®] 5% DIF at a dosage of 2 g/kg body weight (IVIG 2 g/kg arm), Flebogamma[®] 5% DIF at a dosage of 1 g/kg body weight (IVIG 1g/kg arm), and Normal Saline Solution (placebo) will be administered every 4 weeks, with each dose being

administered over a dosing period of 2 consecutive days (Day 1 and Day 2) up to 13 infusions visits, that is, 26 intravenous infusions.

For the purpose of maintaining the treatment blind, the volume of each administration of investigational product in the IVIG 1 g/kg and placebo arms will be equivalent to that for the IVIG 2 g/kg arm so that all subjects receive the same total dose volume for all treatment arms. The total volume for each dose of investigational product will be administered over 2 consecutive days as follows:

- IVIG 2 g/kg arm A total dose of 2 g/kg of body weight of Flebogamma® 5% DIF will be administered over 2 consecutive days.
- IVIG 1 g/kg arm A total dose of 1 g/kg of body weight of Flebogamma[®] 5% DIF will be administered on 1 day, and a total dose of 20 mL/kg of body weight Normal Saline Solution (equivalent volume of 1 g/kg of body weight Flebogamma® 5% DIF infusions) will be administered on a separate day, for a total dosing period of 2 consecutive days. The order of 1 g/kg of body weight of Flebogamma® 5% DIF or 20 mL/kg of body weight Normal Saline Solution infused on 2 consecutive days will be randomly determined for each subject by the IWRS, which will remain the same for the subject for all infusion visits during the treatment period.
- Placebo arm A total dose of 40 mL/kg of body weight Normal Saline Solution (equivalent volume of 2 g/kg of body weight Flebogamma® 5% DIF infusions) will be administered over 2 consecutive days.

Randomized Treatment Assignment	Day 1 (Day 1 Dose per IWRS Randomization list)	Day 2 (Day 2 Dose per IWRS Randomization list)
IVIG 2 g/kg	1g/kg Flebogamma® 5% DIF	1g/kg Flebogamma® 5% DIF
IVIG 1 g/kg	1g/kg Flebogamma [®] 5% DIF OR 20 mL/kg Normal Saline as determined by the IWRS (the opposite treatment as Day 2)	1g/kg Flebogamma [®] 5% DIF OR 20 mL/kg Normal Saline as determined by the IWRS (the opposite treatment as Day 1)
Placebo	20 mL/kg Normal Saline	20 mL/kg Normal Saline

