5.1 Data Handling

Unless otherwise noted, if an observation is missing at a specific scheduled visit/timepoint, the value at that visit will not be imputed and will be set to missing in summary tables.

Baseline will be defined as the measurement taken at the Enrollment Visit (EV)/Infusion Visit 1 (IV1) or the last measurement taken prior to the start of the study treatment if the parameter is not measured at the Enrollment Visit (EV)/Infusion Visit 1 (IV1) or there are multiple observations for the parameter at the Enrollment Visit (EV)/Infusion Visit 1 (IV1).

For table summaries, the data will be presented at the scheduled visits according to protocol. For early terminated subjects, the termination visit occurred at End of Study will be remapped to the subject's next scheduled visit for analysis and summary. Any data collected at the unscheduled visits will be listed in data listings.

5.1.1 **VAS Correction**

For cases where VAS was recorded on the scale sizes of X(mm) other than 100mm, the VAS score will be recalculated as

$$VAS_{=}VAS_{recorded} * \frac{100}{X}$$

The tracker file "IG1104 VAS scale issue 100 mm.xlsx" includes all the protocol deviations of VAS records with scales other than 100mm. The adjusted VAS score will be implemented for the cases included in the tracker file. The unadjusted and adjusted VAS scores will be presented in the relevant CSR listing with a flag to indicate which VAS scores were adjusted. A footnote will be included to explain the rescaling of the VAS scores.

5.2 **Analysis Populations**

In this study, three analysis populations are defined as:

Intent to treat (ITT) population

The Intent-to-treat (ITT) population consists of all subjects randomized.

Per-protocol (PP) population

The Per-protocol (PP) population consists of all subjects in the ITT population who have received at least 8 infusions, without having 2 consecutive missed infusions of any investigational product (test or placebo) during the treatment period, have baseline and at least one post-baseline measures of the 2MWD, and have no critical or major protocol deviations that might have impact on the primary efficacy assessment (as determined at a data review meeting prior to database lock and unblinding).

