9.2 Treatment Compliance

Treatment volume compliance will be calculated as total volume infused * 100% / total volume prepared during the study. The total volume prepared and dispensed by pharmacist is the intended dose volume a subject should be given based on the body weight.

Treatment infusion compliance will be calculated as the number of actual infusions * 100% / number of infusions expected or planned.

The treatment compliance and infusion compliance will be listed and summarized by treatment arm and study stage. Overall compliance (treatment compliance x infusion compliance) will be listed and summarized by treatment arm and study stage. The number of subjects with compliance between 80% and 120% will be calculated.

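### The per-protocol set counts a visit with only Day 1 given as received, although saline-first subjects in the 1 g/kg arm get no IVIG at such a visit, and the exposure tables cannot show which product was missed

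*Protocol*

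**What the plan says.** Protocol 7.1.1 defines a missed infusion by the absence of any product: "A missed infusion will occur when a subject will not be administered with any dose of the investigational product at the scheduled infusion visit". It then deals with a half-completed visit: "If subject receives the investigational product at Day 1 but does NOT receive at Day 2, this will NOT be considered a missed visit". Saline is not outside that definition, because Protocol 7.1 says that Flebogamma and "Normal Saline Solution (placebo) will be used as investigational products".

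In the 1 g/kg arm, Protocol 4.4.2.3 assigns IVIG to one day and saline to the other. The IWRS draws the order at random for each subject, and Protocol 7.1 says of that order: "which will remain the same for the subject for all infusion visits during the treatment period". The schedule is "up to 13 infusions visits, that is, 26 intravenous infusions".

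SAP 5.2 takes into the PP set those ITT subjects "who have received at least 8 infusions, without having 2 consecutive missed infusions of any investigational product (test or placebo"). They must also have a baseline and a post-baseline 2MWD and no critical or major deviation affecting the primary assessment. The listed deviations use the same missed-infusion limits, and the list is open-ended. Protocol 10.6.1 agrees.

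SAP 9.2 measures compliance by volume: "Treatment volume compliance will be calculated as total volume infused * 100% / total volume prepared during the study". Its next sentence equates the prepared volume with the intended weight-based volume. It adds infusion compliance (actual over expected infusions), the product of the two, and a count of subjects between 80% and 120%. SAP 9.3 summarises duration, number of infusions and litres infused.

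**The concern.** The missed-visit rule does not look at the product. That is harmless where both days carry the same solution, but in the 1 g/kg arm they do not. A Day-1-only visit there can mean the whole assigned dose or none of it, depending on an order the blinded team cannot see. The PP criteria adopt this count and ask only for infusions of test or placebo product, so no listed criterion requires a subject in an active arm to have received IVIG.

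At stake is the reading of the PP repeat of the primary analysis (SAP 10.2), whose purpose is to show the 2MWD effect in subjects treated broadly as assigned. The misclassification differs by arm and, within the 1 g/kg arm, by day order, so it blurs the contrast the PP analysis is meant to check. Partial visits are foreseeable: Protocol 7.1.1 has a rule for them, and Protocol 4.4.4.3 lets staff stop an infusion without resuming it.

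**Working it through.** **Reproducing the plan's count.** 52 weeks / 4 weeks = 13 visits, and 13 × 2 days = 26 infusions, as Protocol 7.1 states.

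**One Day-1-only visit.** Volume infused is 20 of 40 mL/kg in every arm. IVIG received against the assigned dose:
- 1 g/kg arm, saline-first: 0 of 1 g/kg = 0%
- 1 g/kg arm, IVIG-first: 1 of 1 g/kg = 100%
- 2 g/kg arm: 1 of 2 g/kg = 50%

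All three score as not missed.

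**Over the treatment year.** Let k of the 13 visits be Day-1-only, with all other infusions complete, body weight constant, and the volume denominator equal to the full intended two-day volume.
- Volume compliance = (26 − k)/26
- IVIG received, saline-first 1 g/kg = (13 − k)/13
- IVIG received, IVIG-first 1 g/kg = 100%
- IVIG received, 2 g/kg = (26 − k)/26

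| k | Volume compliance, all arms | IVIG, saline-first 1 g/kg | IVIG, IVIG-first 1 g/kg | IVIG, 2 g/kg |
|---|---|---|---|---|
| 1 | 96.2% | 92.3% | 100% | 96.2% |
| 5 | 21/26 = 80.8% | 8/13 = 61.5% | 100% | 80.8% |
| 6 | 76.9% | 53.8% | 100% | 76.9% |
| 13 | 50.0% | 0% | 100% | 50.0% |

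Volume compliance tracks the IVIG dose in the 2 g/kg arm. In the 1 g/kg arm it overstates the dose for saline-first subjects and understates it for IVIG-first subjects.

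**PP exposure.** At k = 13 a saline-first subject has 0 missed visits and 13 infusions. The minimum of 8 is met whether the unit is visits or single infusions, so the subject passes the exposure criteria with no IVIG.

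**Overall compliance.** If infusions are counted as 13 visits, infusion compliance stays at 100% and overall compliance equals volume compliance: 80.8% at k = 5 and 50% at k = 13. If they are counted as 26, overall compliance is ((26 − k)/26)²: 85.2% at k = 2, 78.3% at k = 3, 65.2% at k = 5 and 25% at k = 13. A saline-first subject thus stays at or above 80% for up to 5 such visits under the first unit and up to 2 under the second. SAP 9.2 does not say which unit applies.

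**Possible size in the PP effect (illustration only).** The documents give neither the order ratio nor the frequency of Day 2 omissions. Assume a 1:1 order (42/2 = 21 saline-first subjects in Stage 1). Assume also that a fraction f of them receives in effect no IVIG, stays in the PP set and changes as placebo does. The planned 6 m difference becomes 6 × (1 − 0.5f): 5.85 m at f = 5%, 5.7 m at 10%, 5.4 m at 20%. With the planned SD of 11 m and 42 per arm, the standard error is 11 × √(2/42) = 2.4 m, so the shift at f = 10% is 0.3/2.4, about one-eighth of a standard error.

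**The case against.** The strongest reply is that the SAP does not hide these subjects. A reader might infer that someone who received no IVIG appears as fully treated in the compliance tables. The documents do not support that. SAP 9.2 equates the denominator with the intended weight-based volume, so the k = 13 subject shows 50% volume compliance and 50% or 25% overall, well outside the 80% to 120% band. A reading of 100% would require the denominator to leave out a Day 2 bag that was never prepared, which goes against that sentence. Volumes are also recorded in the eCRF and listed, so Day 2 omissions are visible. What remains is narrower: no planned summary separates IVIG from saline.

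A reader might also infer that the choice between doses is affected. It is not. The interim analysis (SAP 5.4) takes subjects who completed the treatment year or have a 2MWD at six months or later, with no PP criterion, and the primary analysis is ITT. Lost IVIG would dilute those results however the PP set is worded.

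Third, the deviation list is open-ended, and the blinded review meeting can see that Day 2 was not given. It could exclude repeat cases, but nothing compels it to, and it cannot see day order.

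Finally, a both-days rule also fails IVIG-first subjects who missed only saline. That is correct and is a cost of the fix.

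**Conclusion.** The point holds for the PP definition and for what the exposure tables can show. A saline-first subject in the 1 g/kg arm can meet the PP exposure criteria with visits, in the extreme all 13, that delivered no IVIG. The tables report the lost volume but not the lost product; the gap at k = 5 is 80.8% against 61.5%.

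Its reach is limited. It bears on a sensitivity analysis and on descriptive exposure, in Stage 1, and in Stage 2 for the 1 g/kg arm only if that dose is carried forward. The ITT primary analysis and the dose selection rule stand as they are. Thirteen Day-1-only visits is a constructed extreme, and isolated lost visits are more likely. With the frequency of Day 2 omissions unknown, the effect on the PP estimate cannot be stated; the illustration suggests it would be small unless omissions were common. The percentages assume constant weight, otherwise complete infusions and the intended-volume denominator. The change is worth making because the rule misclassifies by arm and the data to correct it are already collected.

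**What to change.** Leave the clinical missed-visit rule in Protocol 7.1.1 as it is and change the analysis definitions only.

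1. **SAP 5.2.** For PP exposure, count an infusion visit as received only if both day infusions were given, applied blind and identically in all arms. State whether a partly infused day counts as given, and whether the missed-infusion limits in the deviation list use the same count. With days infused in full, the minimum of 8 visits then guarantees a saline-first PP subject at least 8/13 = 61.5% of the assigned IVIG, where the present wording guarantees none.
2. **SAP 9.2 and 9.3.** After unblinding, derive the IVIG g/kg actually received from the recorded volumes and the IWRS day order. Summarise it by arm against the assigned dose, per visit and in total.

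As clarification only, say in SAP 9.2 that the denominator is the planned two-day volume whether or not a bag was prepared, and whether infusions are counted out of 13 or 26.

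The cost is SAP wording and one derived exposure variable, with no new data collection. The PP set may be smaller and will lose some IVIG-first subjects who missed only saline. The new exposure summary would show how many had in fact received their full dose.
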